# 6.3.1.4 Dose modification and management guideline for visual changes suspected to be related to dabrafenib and/or trametinib treatment

Episodes of visual changes have been observed in patients receiving trametinib, dabrafenib, and combination therapy. An ophthalmologist is to be consulted if changes in vision develop. However, if the visual changes are clearly unrelated to study treatment (e.g., allergic conjunctivitis), then monitor closely as it may be reasonable to defer ophthalmic examination.

Special attention should be given to retinal findings (e.g., retinal pigment epithelial detachment (RPED) or retinovascular abnormalities (i.e., branch or central retinal vein occlusions (RVO). Treatment emergent cases of RVO and RPED are to be reported as SAEs.

Guidelines for dose modifications and management for visual changes and/or ophthalmic examination findings considered to be related to study treatment are provided in Table 6-19 and Table 6-20.

Treatment with dabrafenib has been associated with the development of uveitis, including iritis. Monitor patients for visual signs and symptoms (such as, change in vision, photophobia and eye pain) during therapy. Guidelines for dose modifications and management for uveitis, including iritis considered to be related to study treatment are provided in Table 6-21.

Table 6-19 Mandatory dose modification and recommended clinical management for visual changes and/or ophthalmic examination findings suspected to be related to trametinib treatment

| Visual changes (Eye disorders – Other, CTCAE Version 4.03, retinal, and similar)   |  |  |  |
|--|--|--|--|
| Grade  | Recommended adverse event management guidelines                            | Mandatory dose modification requirements   |  |
| Grade 1  If visual changes are clearly unrelated to study treatment (e.g. allergic conjunctivitis), monitor closely but ophthalmic examination is not required | Initiate local therapy and consult ophthalmologist within 7 days of onset. | 
 
If dilated fundus examination cannot be performed within 7 days of onset, interrupt trametinib until RPED and RVO can be excluded by retina specialist/ophthalmologist. Continue dabrafenib.
 
If RPED and RVO excluded, continue (or restart) trametinib at same dose level
 
If RPED suspected or diagnosed: see RPED dose modification Table 6-20; report as SAE if diagnosed.
 
If RVO diagnosed: Permanently discontinue trametinib and report as SAE.
 
 |  |

| Visual changes (Eye | e disorders – Other, CTCAE Version 4                           | .03, retinal, and similar)  |  |  |  |  |  |  |
|---------------------|--|---|--|--|--|--|--|--|
| Grade               | Recommended adverse event management guidelines                | Mandatory dose modification requirements  |  |  |  |  |  |  |
| Grade 2 and Grade 3 | Initiate local therapy and consult ophthalmologist immediately | Interrupt trametinib. Dabrafenib may be continued at the current dose.                      |  |  |  |  |  |  |
|                     |  | If RPED and RVO excluded, restart trametinib at same dose level.                            |  |  |  |  |  |  |
|                     |  | If RPED diagnosed, see RPED dose modification in Table 6-20; report as SAE.                 |  |  |  |  |  |  |
|                     |  | If RVO diagnosed: Permanently discontinue trametinib and report as SAE.                     |  |  |  |  |  |  |
| Grade 4             | Initiate local therapy and consult ophthalmologist immediately | Interrupt trametinib. Dabrafenib may be continued at the same dose.                         |  |  |  |  |  |  |
|                     |  | If RPED and RVO excluded, consider restarting trametinib at the same or reduced dose level. |  |  |  |  |  |  |
|                     |  | If RVO diagnosed, permanently discontinue trametinib and report as SAE.                     |  |  |  |  |  |  |

Table 6-20 Mandatory dose modification and recommended clinical management for retinal pigment epithelial detachments (RPED) suspected to be related to trametinib treatment

| Re | Retinal pigment epithelial detachments (RPED)                                 |   |  |  |  |  |  |  |  |  |  |  |  |  |  |
|----|---|---|--|--|--|--|--|--|--|--|--|--|--|--|--|
| Gr | ade   | Recommended adverse event management guidelines | Mandatory dose modification requirements   |  |  |  |  |  |  |  |  |  |  |  |  |
| •  | Grade 1 (Asymptomatic; clinical or diagnostic observations only)              | If RPED worsens follow instructions below.      | Continue treatment with retinal evaluation monthly until resolution.   |  |  |  |  |  |  |  |  |  |  |  |  |
| •  | Grade 2-3 RPED (Symptomatic with mild to moderate decrease in visual acuity). | Retinal evaluation monthly.                     | 
 
Interrupt trametinib.
 
If improved to ≤ Grade 1, restart trametinib at a lower dose.
 
 |  |  |  |  |  |  |  |  |  |  |  |  |

Table 6-21 Mandatory dose modification and recommended clinical management for uveitis, including iritis suspected to be related to dabrafenib treatment

| Grade           | Recommended adverse event management guidelines                | Mandatory dose modification requirements   |
|-----------------|--|--|
| Grade 1         | Initiate local therapy and consult ophthalmologist immediately | 
 
Continue dabrafenib and trametinib
 
If no response to local treatment within 7 days, interrupt dabrafenib. Once uveitis resolves, restart dabrafenib
 
Continue trametinib
 
  |
| Grade 2, 3 or 4 | Initiate local therapy and consult ophthalmologist immediately | 
 
Interrupt dabrafenib
 
If ≥ grade 2 uveitis (including iritis and iridocylitis) lasts >6 weeks on local treatment and dabrafenib has not been restarted, permanently discontinue dabrafenib
 
Continue trametinib
 
 |

# 6.3.1.5 Dose modification and management guideline for new malignancies suspected to be related to dabrafenib and/or trametinib treatment

#### **New Malignancies: Cutaneous and Non-cutaneous**

#### 6.3.1.5.1 Cutaneous malignancies

Cutaneous squamous cell carcinoma (CuSCC), keratoacanthomas (KA) and new primary melanomas have been observed in patients treated with dabrafenib and dabrafenib/trametinib combination therapy. These treatment-related lesions should be surgically removed according to institutional practices. Dose modification or interruption of study treatment is not required for cuSCC, KA, or new primary melanoma, however cuSCC and new primary melanoma are to be reported as a SAE. In addition, a biopsy of the lesion should be taken, where possible, and submitted for further analyses and a summary of the results submitted to Novartis. Patients should be instructed to immediately inform their physician if new lesions develop. Skin examinations are to be performed prior to initiation of study treatment and throughout therapy as detailed in the Visit Evaluation Schedule (Table 7-1, Table 7-2 for LGG crossover patients or Table 7-3). Monitoring will occur at 3 and 6 months following discontinuation of study treatment or until initiation of another anti-neoplastic therapy. Monitoring of the skin can be performed by a qualified local physician at the discretion of the investigator during non-clinic visits. If possible, the same local physician should perform each exam throughout the study to ensure consistency between evaluations.

## 6.3.1.5.2 Non-Cutaneous Malignancies

In vitro experiments have demonstrated paradoxical activation of MAP-kinase signaling in *BRAF* wild type cells with RAS mutations when exposed to *BRAF* inhibitors, which may lead to increased risk of non-cutaneous malignancies in patients treated with dabrafenib. Cases of RAS-driven malignancies have been seen with *BRAF* inhibitors. Consider the benefits and risks before continuing treatment with dabrafenib in patients with a non-cutaneous malignancy that has a RAS mutation. No dose modification of trametinib is required when taken in combination with dabrafenib.

New non-cutaneous malignancies are to be reported as a SAE. A biopsy of the new malignancy should be taken, where possible, and submitted for further analyses including RAS mutation status with the results provided to Novartis.

Patients should be monitored for secondary malignancy as clinically appropriate. This may include review of signs and symptoms and physical exam. If there is clinical concern or possible increased risk for the development of an occult secondary malignancy, additional imaging such as whole-body MRI may be appropriate. Following discontinuation of dabrafenib, monitoring for non-cutaneous secondary/recurrent malignancies should continue for up to 6 months or until initiation of another anti-neoplastic therapy.

## 6.3.1.6 Dose modification and management guideline for hyperglycemia

Hyperglycemia requiring an increase in the dose of, or initiation of insulin or oral therapy can occur with dabrafenib. Monitor serum glucose levels as clinically appropriate during treatment with dabrafenib in patients with pre-existing diabetes or hyperglycemia.

Advise patients to report symptoms of severe hyperglycemia such as excessive thirst or any increase in the volume or frequency of urination.

#### 6.3.1.7 Guidelines for prolonged QTc

Guidelines for dose modification and stopping criteria due to QTc-prolongation are provided in Table 6-22.

If ECG results demonstrate a prolonged QT interval (QTcF ≥501 msec), obtain two or more additional ECGs over a brief period, and then use the average QTc values of the three ECGs to determine if study treatment should be interrupted or discontinued. If the QTc prolongation resolves to Grade 1 or baseline, the patient may resume study treatment if the investigator determines that the patient may benefit from further treatment. This determination must be documented by the investigator in the patient's medical record.

Table 6-22 Withholding and Stopping Criteria for QTc-Prolongation

#### QTc Prolongation QTcF ≥501 msec Based on average QTc value of triplicate ECGs

#### **Action and Dose Modifications**

- Assess the quality of the ECG recording and the QT value and repeat if needed
- Interrupt dabrafenib and trametinib (study treatments) until QTcF prolongation resolves to Grade 1 or baseline
- Test serum potassium, calcium, phosphorus and magnesium. If abnormal, correct per routine clinical practice to within normal limits.
- Review concomitant medication associated with QT prolongation, including drugs with a "known", "possible" or "conditional risk of Torsade de pointes" and drugs with the potential to increase the risk of study drug exposure related to QT prolongation
- If event resolves to grade 1 or baseline, patient may restart study treatments at current dose level if patient may benefit from further treatment
- If event does not resolve within 28 days, permanently discontinue study treatments. Consider evaluation with cardiologist.
- If event recurs, permanently discontinue study treatments. Consider evaluation with cardiologist.

Abbreviations: ECG = electrocardiogram; msec = milliseconds; QTcF = QT duration corrected for heart rate by Fredericia formula.

#### 6.3.1.8 Left Ventricular Ejection Fraction Stopping Criteria

Decreases of the left-ventricular-ejection-fraction (LVEF) have been observed in patients receiving trametinib monotherapy and in combination with dabrafenib. Therefore, ECHOs must be performed to assess cardiac ejection fraction in regular intervals as outlined in the Visit Evaluation Schedule (Table 7-1, Table 7-2 for LGG crossover patients, Table 7-3). Dose modification guidance and stopping criteria for LVEF decrease are provided in Table 6-23. ECHO to be performed at baseline and at follow up visit(s).

Table 6-23 Mandatory dose modification and recommended clinical management for LVEF suspected to be related to dabrafenib and/or trametinib treatment

| LVEF-drop (%) & clinical symptoms  | Recommended adverse event management guidelines   | Mandatory dose modification
requirements  |  |  |  |  |  |
|--|---|--|--|--|--|--|--|
| Asymptomatic: Absolute decrease of >10% in LVEF compared to baseline and ejection fraction below the institution's LLN | 
 
Closely monitoring LVEF via ECHO, repeat ECHO within 2 weeks*.
 
If the LVEF recovers within 4 weeks (defined as LVEF ≥LLN and absolute decrease ≤10% compared to baseline)
 
Repeat ECHO 2, 4, 8 and 12 weeks after re-start; continue in intervals of 12 weeks thereafter.
 
If repeat LVEF does not recover within 4 weeks.
 
Consult with cardiologist
 
Repeat ECHO after 2, 4, 8, 12, and 16 weeks or until resolution
 
 | 
 
Report as SAE.
 
Interrupt trametinib.
 
If the LVEF recovers, restart trametinib reduced by one dose level and continue dabrafenib at the same dose level.
 
More than two occurrence, permanently discontinue trametinib.
 
Permanently discontinue trametinib if repeat LVEF does not recover within 4 weeks.
 
 |  |  |  |  |  |
| Symptomatic: Resting LVEF 39-20% or >20% absolute reduction from baseline resting LVEF <20%                            | 
 
Consult with cardiologist.
 
Repeat ECHO after 2, 4, 8, 12, and 16 weeks or until resolution.
 
  | 
 
Report as SAE.
 
Permanently discontinue trametinib.
 
Interrupt dabrafenib
 
Restart dabrafenib if LVEF recovers including resolution of symptoms.
 
   |  |  |  |  |  |

\* If ECHO does not show LVEF recovery after 2 weeks, repeat ECHO 2 weeks later.

#### 6.3.1.9 Cardiac valvular toxicity stopping criteria

**Grade 2:** Patients who have an asymptomatic, moderate regurgitation or stenosis by ECHO (Grade 2 mitral/tricuspid/aortic valvular toxicity) should temporarily discontinue dabrafenib and trametinib and have a repeat evaluation by ECHO within 1 week. ECHO should be repeated every 1-2 weeks for 4 weeks or until valve recovery to baseline.

- If the valve recovers to baseline any time during the next 4 weeks, the patient may be restarted at a reduced dose(s). For such patients, monitoring of the valve via ECHO will then be performed 2 and 4 weeks after re-challenge, and every 4 weeks thereafter for 12 weeks and then per protocol.
- If repeat ECHO does not reveal valve recovery to baseline within 4 weeks, then the patient should permanently discontinue dabrafenib and trametinib. The valve should continue to be monitored via ECHO every 4 weeks for 16 weeks or until resolution.

**Grade 3:** Patients with a Grade 3 valvular toxicity (symptomatic, severe regurgitation/stenosis by imaging, with symptoms controlled by medical intervention) must discontinue dabrafenib and trametinib. Valvular toxicity should continue to be monitored every 4 weeks for 16 weeks or until resolution. If recovery occurs (return to baseline via imaging AND symptom resolution) within 4 weeks and the patient is receiving unequivocal clinical benefit from the study treatment

as per documented investigator assessment, the patient may restart dabrafenib and trametinib at a reduced dose.

**Grade 4:** Patients with a Grade 4 valvular toxicity [life-threatening consequences; urgent intervention indicated (e.g., valve replacement, valvuloplasty)] must **permanently discontinue** dabrafenib and trametinib.

## 6.3.1.10 Dose modification and management guideline for skin rash

Guidelines for dose modification and management of skin rash considered to be related to study treatment by the investigator are provided in Table 6-24.

Table 6-24 Mandatory dose modifications and recommended clinical management guidelines for rash

| Rash Events (NCI-CTCAE v                       | ement guidelines for rash   |  |  |  |  |  |  |  |
|--|---|--|--|--|--|--|--|--|
| Grade  | Recommended adverse event management guidelines   | Mandatory dose modification requirements   |  |  |  |  |  |  |
| Grade 1: Rash covering < 10% body surface area | 
 
Initiate prophylactic and symptomatic treatment measures.
 
Consider use of topical corticosteroids or urea containing creams in combination with oral antipruritics or moderate strength topical steroid (hydrocortisone 2.5% cream or fluticasone propionate 0.5% cream)
 
Reassess after 2 weeks
 
 | Continue dabrafenib and trametinib at the same dose.   |  |  |  |  |  |  |
| Grade 2: 10-30% of body surface area           | 
 
If tolerable, as per Grade 1
 
If intolerable, initiate systemic steroids (0.5 to 1 mg/kg/day prednisone or equivalents)
 
If symptoms persist or recur consider skin biopsy.
 
   | If tolerable, continue dabrafenib and trametinib at the same dose.      If intolerable:     1st occurrence      Interrupt dabrafenib and trametinib until ≤ Grade 1, and reduce dabrafenib and trametinib to the next dose level. Re-escalation of the patient's dose is recommended if criteria in Section 6.3.1 are met.   |  |  |  |  |  |  |
| Grade 3: More than 30% of body surface area    | 
 
Obtain a skin biopsy and dermatology consult.
 
Initiate therapy with high dose steroids (1 to 2 mg/kg/day prednisone or equivalents)
 
  | 1st occurrence Interrupt dabrafenib and trametinib until ≤ Grade 1, and reduce dabrafenib and trametinib to the next dose level. Re-escalation of the patient's dose is recommended if criteria in Section 6.3.1 are met.  2nd occurrence Interrupt dabrafenib and trametinib until ≤ Grade 1 or baseline. Once recovered, reduce dabrafenib and trametinib to the next dose level. Re-escalation of the |  |  |  |  |  |  |

Permanently discontinue dabrafenib and trametinib.

Grade 4: Life-threatening

| Rash Events (NC | -CTCAE v4.03)                                      |  |
|-----------------|--|--|
| Grade           | Recommended adverse event
management guidelines | Mandatory dose modification requirements   |
|                 |  | patient's dose is recommended if criteria in Section 6.3.1 are met.  |
|                 |  | 3 rd occurrence   |
|                 |  | • Interrupt dabrafenib and trametinib until ≤ Grade 1 or baseline. Once recovered, reduce dabrafenib and trametinib to the next dose level, if available as dose level -2. If already at dose level -2 at time of occurrence, permanently discontinue dabrafenib and trametinib. Reescalation of the patient's dose is recommended if criteria in Section 6.3.1 are met. |
|                 |  | 4 th occurrence   |
|                 |  | 
 
Permanently discontinue
dabrafenib and trametinib.
 
   |

## 6.3.1.11 Management of Severe cutaneous adverse reactions (SCAR)

Same as Grade 3

Cases of severe cutaneous adverse reactions (SCARs), including Stevens-Johnson syndrome, and drug reaction with eosinophilia and systemic symptoms (DRESS), which can be life-threatening or fatal, have been reported during treatment with dabrafenib in combination with trametinib. Before initiating treatment, patients should be advised of the signs and symptoms and monitored closely for skin reactions. If signs and symptoms suggestive of SCARs appear, dabrafenib and trametinib should be permanently discontinued..

## 6.3.1.12 Management Guidelines for Additional AEs

- Palmar Plantar Erythrodysesthesia (PPES) Measures for PPES should include:
  - Lifestyle modification: avoidance of hot water, traumatic activity, constrictive footwear, or excessive friction on the skin and the use of thick cotton socks and gloves, and shoes with padded insoles
  - Symptomatic treatments: apply moisturizing creams frequently, topical keratolytics (e.g. urea 20-40 % cream, salicylic acid 6%, tazarotene 0.1% cream, fluorouracil 5% cream), clobetasol propionate 0.05% ointment for erythematous areas, topical lidocaine 2%, and / or systemic pain medication such as nonsteroidal anti-inflammatory drugs, codeine, and pregabalin for pain.
  - Dose modification may also be required (refer to Table 6-9)
- Pancreatitis In the event of abdominal pain or suspected pancreatitis, amylase and lipase laboratory samples should be collected for confirmation of the diagnosis. If pancreatitis is suspected, dabrafenib should be held until recovery. Trametinib dosing

may continue. Patients should be closely monitored when re-starting dabrafenib after an episode of pancreatitis

# 6.3.1.13 Dose modification and management guideline for hypertension suspected to be related to dabrafenib and/or trametinib treatment

Increases in blood pressure have been observed in patients receiving trametinib. For adequate monitoring and management of hypertension, all blood pressure assessments should be performed under the following optimal conditions:

- the patient has been seated with back support, ensuring that legs are uncrossed and flat on the floor
- the patient is relaxed comfortably for at least 5 minutes
- restrictive clothing has been removed from the cuff area and the right cuff size has been selected
- the patient's arm is supported so that the middle of the cuff is at heart level
- the patient remains quiet during the measurement.

In patients with an initial blood pressure reading within the hypertensive range, a second reading should be taken at least 1 minute later, with the 2 readings averaged to obtain a final blood pressure measurement. The averaged value should be recorded in the eCRF.

Persistent hypertension is defined as an increase of systolic or diastolic blood pressure (SBP, DBP) > 95th percentile for age in three consecutive visits with blood pressure assessments from two readings collected as described above. Visits to monitor increased blood pressure can be scheduled independently from the protocol visits outlined in Table 7-1, Table 7-2 for LGG crossover patients or Table 7-3. Ideally, subsequent blood pressure assessments should be performed within one week.

Asymptomatic hypertension is defined as an increase of SBP or DBP >95th percentile in the absence of headache, light-headedness, vertigo, tinnitus, episodes of fainting or other symptoms indicative of hypertension.

For patients experiencing an increase in systolic and/or diastolic blood pressure that is persistent and may be associated with the study treatment, recommendations for dose modifications and management of hypertension are described below in Table 6-25.

Table 6-25 Mandatory dose modification and recommended clinical management for hypertension

| Hypertension (NCI-CTCAE 4.0   | 3)  |  |  |  |  |  |  |
|---|---|--|--|--|--|--|--|
| Severity  | Recommended adverse event management guidelines   | Mandatory dose modification requirements                                     |  |  |  |  |  |
| 

(Scenario A)

Asymptomatic and

                           | 
 
Adjust current or initiate new antihypertensive medication.
 
   | 
 
Continue dabrafenib and
trametinib at the same dose.
 
 |  |  |  |  |  |
| persistent a increase of
SBP or DBP >95 th
percentile | Titrate antihypertensive
medication(s) during the next 2
weeks as indicated to achieve well-                                    |  |  |  |  |  |  |
| 
 
Clinically significant
 
  | controlled b BP  |  |  |  |  |  |  |
| increase in DBP of 20
mmHg (but still below 100
mmHg).                      | 
 
If BP is not well controlled within 2
weeks, recommended to refer to a
specialist and go to scenario (B).
 
 |  |  |  |  |  |  |

| Hypertension (NCI-CTCAE 4.0  | 3)   |   |
|--|--|---|
| Severity   | Recommended adverse event management guidelines  | Mandatory dose modification requirements  |
| (Scenario B)  • Asymptomatic increase of SBP or DBP >99 th percentile, or Failure to achieve well-controlled BP within 2 weeks in Scenario A      | 
 
Adjust current or initiate new antihypertensive medication(s).
 
Titrate antihypertensive medication(s) during the next 2 weeks as indicated to achieve well-controlled BP.
 
             | 
 
Interrupt dabrafenib and trametinib if clinically indicated.
 
Once BP is well controlled restart dabrafenib and trametinib reduced by one dose level.
 
 |
| Symptomatic c hypertension or   | Adjust current or initiate new antihypertensive medication(s)  | 
 
Interrupt dabrafenib and trametinib.
 
  |
| Persistent increase in
SBP or DBP >99 th
percentile, despite
antihypertensive
medication and dose
reduction of study
treatment. | 
 
Titrate antihypertensive medication during the next 2 weeks as indicated to achieve well-controlled BP.
 
Referral to a specialist for further evaluation and follow-up is recommended.
 
 | 
 
Once BP is well controlled,
restart dabrafenib and
trametinib reduced by one
dose level.
 
  |
| Refractory hypertension
unresponsive to above
interventions or
hypertensive crisis.   | Continue follow-up per protocol.   | Permanently discontinue
dabrafenib and trametinib.   |

- a. Hypertension detected in two separate readings during up to three consecutive visits.
- b. Well-controlled blood pressure defined as SBP and DBP ≤ 95th percentile in two separate readings during up to three consecutive visits.
- Symptomatic hypertension defined as hypertension aggravated by symptoms (e.g., headache, light-headedness, vertigo, tinnitus, episodes of fainting) that resolve after the blood pressure is controlled within the normal range.

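### Table 6-25, Scenario A has no upper percentile limit, so an asymptomatic child persistently above the 99th percentile can meet both Scenario A (same dose) and Scenario B (lower dose on restart)

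*Protocol*

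**What the plan says.** Table 6-25 (protocol section 6.3.1.13) has a severity column, a column of recommended management and a column of mandatory dose modifications.

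- **Scenario A, entry.** The first bullet is an asymptomatic and "persistent a increase of SBP or DBP >95 th percentile" (the stray letter is the marker for footnote a). The second bullet is a clinically significant "increase in DBP of 20 mmHg (but still below 100 mmHg"). No and/or joins them.
- **Scenario A, action.** Mandatory: "Continue dabrafenib and trametinib at the same dose". Recommended: "Adjust current or initiate new antihypertensive medication", then titration over two weeks, moving to Scenario B if control is not reached.
- **Scenario B, entry.** "Asymptomatic increase of SBP or DBP >99 th percentile, or Failure to achieve well-controlled BP within 2 weeks in Scenario A".
- **Scenario B, action.** Mandatory: "Interrupt dabrafenib and trametinib if clinically indicated", and then "Once BP is well controlled restart dabrafenib and trametinib reduced by one dose level".
- **Footnote b.** "Well-controlled blood pressure defined as SBP and DBP ≤ 95 th percentile in two separate readings", taken over up to three consecutive visits.

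The text before the table directs it to increases that are persistent and possibly related to treatment. It defines persistent hypertension as pressure above the 95th percentile for age at three consecutive visits. Footnote a instead speaks of two separate readings during up to three consecutive visits. Inclusion criterion 1 (section 5.2) sets the age range at 12 months to under 18 years.

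**The concern.** Above the 95th percentile includes above the 99th. With no upper limit in Scenario A, an asymptomatic child persistently above the 99th percentile satisfies its first bullet and also the entry criterion of Scenario B. The two mandatory columns then say different things about dose, and no sentence in the table ranks the rows.

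The second bullet adds to the uncertainty. It is a fixed mmHg rule with no age term, and the table does not say whether it widens or narrows the first bullet.

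Hypertension is an adverse event of special interest (section 8.1.3). Section 6.3.1 allows two dose reductions and requires discontinuation if more are needed. Sections 10.3 and 10.5.1.6 summarise dose reductions and interruptions, the latter as the measure of tolerability. If sites choose different rows for the same pressure, those summaries partly reflect the choice of row.

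**Working it through.** The plan gives no figure to reproduce. The check takes the entry criteria as written and asks which rows each possible presentation meets.

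**Inputs (all from section 6.3.1.13).** SBP band and DBP band, each at or below the 95th percentile, above the 95th up to the 99th, or above the 99th; persistent or not; DBP rise of 20 mmHg or not; DBP below 100 mmHg or not. All profiles are asymptomatic and at first presentation, so failure under Scenario A does not arise. Number of profiles: 3 × 3 × 2 × 2 × 2 = 72. There are 9 pairs of SBP and DBP bands, with 8 profiles each.

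**Pairs by highest band.** Both at or below the 95th: 1 pair (well controlled under footnote b). Highest band between the 95th and 99th: 2 × 2 − 1 = 3 pairs. At least one above the 99th: 9 − 4 = 5 pairs (Scenario B).

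**Three readings of Scenario A.**
1. *Alternatives:* persistent and above the 95th, or the mmHg bullet. Within a pair above the 99th, 4 profiles are persistent and 1 more qualifies by the mmHg bullet alone, giving 5 of 8.
2. *Joint:* both bullets needed. This gives 1 of 8.
3. *Alternatives limited by the lead-in:* only persistent pressures above the 95th enter the table. This gives 4 of 8, all already admitted by the first bullet.

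| Result | Alternatives | Joint | Limited by lead-in |
|---|---|---|---|
| Meets A and B | 5 × 5 = 25 | 5 × 1 = 5 | 5 × 4 = 20 |
| of which only SBP is above the 99th, with DBP at or below the 95th (1 pair) | 5 | 1 | 4 |
| Meets A while at or below the 95th | 1 × 2 = 2 | 0 | 0 |
| Persistent, 95th to 99th, in no row (of 3 × 4 = 12) | 0 | 12 − 3 = 9 | 0 |

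The overlap between A and B appears under every reading. It includes profiles in which only SBP is above the 99th percentile, so it does not depend on any paediatric diastolic norm. Beyond that, each reading has its own defect: possible entry at a well-controlled pressure, a gap, or a second bullet that admits nobody new.

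These are counts of logical combinations. They are not frequencies of patients.

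**The case against.** The strongest reply is that the rows rise in severity, Scenario A hands on to Scenario B, and a child above the 99th percentile belongs in the row that names that limit. Section 6.3.1 supports this: it bases dose modifications on the worst preceding toxicity and tells investigators to err on the side of caution. That makes the higher row the natural reading. It does not settle the point, because the rule is tied to CTCAE grades and the scenarios are not graded. Scenario A also has its own route to Scenario B, failure after two weeks, which a site could read as A first at full dose.

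The dose conflict is also conditional. In Scenario B the interruption is discretionary and the reduction is worded for the restart; without an interruption no reduction is clearly required. A reduction may later be reversed after four well-tolerated weeks with clinical benefit (section 6.3.1). A reader might infer that the rows always differ by one mandatory dose level; the text does not support that. Still, the next row refers to pressure persisting despite a dose reduction, which presupposes an earlier one.

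A reader might also infer that children at a well-controlled pressure will be started on antihypertensives. That needs the bullets to be alternatives, sits awkwardly with the lead-in about persistent increases, and concerns the recommended column, not the mandatory one. It is a possible consequence of the wording and is not established.

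**Conclusion.** The overlap is real and follows from the table's own words: a persistent, asymptomatic pressure above the 99th percentile can meet two rows with different mandatory dose instructions, and the table states no precedence. It covers 25 of 72 logical profiles if the bullets are alternatives, 20 if the lead-in limits them, and 5 if they are joint. The two definitions of persistence are a further, smaller inconsistency.

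Three stronger readings are not supported:

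- That every persistent asymptomatic pressure above the 99th percentile meets both rows. This is so if the bullets are alternatives, with or without the lead-in; under the joint reading only 5 of the 5 × 4 = 20 such profiles do.
- That the figures of 20 and 100 mmHg are an adult rule, or that the overlap has a known width in mmHg. The protocol gives neither the origin of those figures nor any percentile values.
- That every other boundary in the table is a percentile. Later rows also use symptoms, refractory hypertension and hypertensive crisis.

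This is a drafting fault in a mandatory safety rule. Its effect falls on consistency of dosing and on the dose-reduction summaries; no effect on the primary response analysis is shown.

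**What to change.** The sponsor's clinical team should reconcile the entry criteria of Scenarios A and B, the definitions in the text of section 6.3.1.13, and footnotes a and b, so that each reading leads to one row and one mandatory action. In doing so it should state how the two Scenario A bullets combine, which row governs when more than one is met, and which definition of persistence applies. No threshold or dose action is proposed here. The cost is wording in one section and its table at the next amendment; blood pressure and age are already recorded, so no new measurement is needed.
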